# 9.7.3 Describing changes of health profile of patients, assessment of adherence, number of indication related episodes (ACS related events), plus any alterations of the treatment programme in respect of antiplatelet and anticoagulant therapy during the 12 week study observation period

The following relates to Section 8.2 secondary objective 2. Status of indication-related characteristics (alteration of diagnosis and bleeding risk score if available) will be summarised, plus pattern of antiplatelet treatment adherence at the end of the 12 week observation period (as estimated from Medication Possession Ratio) will be summarised. The frequency and reasons for attendance to clinics for review and management of ACS and/or acute hospitalisations (including hospital referrals) will also be summarised, where reported. Alterations in treatment programme (change in dose, other drugs) will be described, as will any reason(s) for changing treatment regimen (including switching) and transition plans to other antiplatelets.

Changes in these indication-related characteristics and treatment details will be examined by comparing values at index and at 12 weeks post index date. Exploratory analysis may include data mining and descriptive measures for describing alterations in treatment programme.

The number of pregnancies, trimester of first exposure and details of births, terminations and miscarriages will be presented. The number of deaths (as recorded in medical charts) in the total cohort for each month of exposure will be calculated. Causes of death will also be described by system-organ class.

Sensitivity analyses will examine any under-reporting using data provided from the patients GP.

<sup>1 For this study, MPR will be defined as: No. days supply held during treatment x 100 No. days supply expected during treatment

Where no. days held will be calculated from information derived from 12 week questionnaire on number of prescriptions and average treatment length of prescriptions (usually given in 7, 14,28,56 day repeats); no. days supply expected will assume chronic use from start to end of study observation or treatment stop date (if stopped)

9.7.4 Quantifying the risk of other major (in any other site not specified in the primary objective) or minor bleeding outcomes (in any site) reported in the 12 week observation period overall (Tables 1 and 2) and, if number of reports are sufficient, in patient subgroups of special interest in first 12 weeks of treatment under conditions of the routine secondary care hospital setting in England and Wales. Also, where possible, to quantify the incidence of other important identified, potential and special risks not mentioned in the primary objective and any other events reported during treatment with rivaroxaban (rivaroxaban cohort only)

The following relates to Section 8.2 secondary objective 3 and exploratory objective 1) and 2) regarding a) other major and minor bleeding outcomes not specified in the primary objectives in both cohorts and b) any other events reported in the 12 week observation period for rivaroxaban cohort only.

For major bleeding events not specified in the primary outcome, each of the individual components of the major bleeding will be summarised. Where an individual has one or more criterion for an individual organ site of interest, this will also be summarised – in such individuals the first report will be regarded as the incident event.

For minor bleeding events, each of the individual associated components (as per Table 1) will be summarised. Where an individual has one or more criterion for a minor bleeding event, this will also be summarised – in such individuals the first event report will be regarded as the incident event.

Analysis of event data for purposes of signal detection includes exploring overall risk and rate for the observation period and time to onset profiles. The methodology provides a numerator (the number of reports of an event) and a denominator (persontime at risk), both collected within a known time frame. This allows for the calculation of crude risks (percent of total valid cohort exposed) and rates (Incidence Densities-ID; person-time incidence rates) for each event separately. Each event may be reported in response to a closed question (for example information on each individual major and/or clinically relevant non-major bleeding risk component), or as free text in response to open questions on the data collection forms. Such analyses will be performed using 'Higher-level' event terms from the MedDRA dictionary where possible. The risk profile of the overall cohorts and sub-group of interest (based on index date characteristics, including whether anticoagulant naïve, rivaroxaban naïve or past (other anticoagulant user) will be described by presenting summary tabulations (by rank) of counts and incidence risk of reported events, and crude event rates (IDs). Calculating and ranking crude ID rates is one of a number of standard quantitative evaluations used in event monitoring methodology for signal generation purposes as part of initial inspection of all event data for general safety surveillance. It is used as a means of alerting early potential signals as priorities for further evaluation. Medical judgment however is also part of this evaluation and prioritization process. Crude Incidence Densities (ID) can be calculated by week in order to quantify rates of events. IDs will be calculated, for each given time period (t), for all events reported in patients who continue to take rivaroxaban for a given time period, or for whom the date of stopping is known. Only the first report of an event in an individual patient is used in the calculation of IDs. They are usually expressed as the number of first reports of an event per 1000 patient-weeks. This assumes the pattern of use is continuous. The numerator will be the first reports of events reported as occurring after the index date and during treatment. For this study, IDs will be calculated for each event for each week as follows:

 $\begin{array}{rcl} ID_t = & \underline{Number \ of \ first \ reports \ of \ an \ event \ during \ treatment \ for \ period \ t \ x \ 1000} \\ & & Number \ of \ patient-weeks \ of \ treatment \ for \ period \ t \end{array} \\ Thus, \ ID_t = & \underline{N_t \ x \ 1000} \\ & & D_t \end{array} \\ where: N_t = & Number \ of \ first \ reports \ of \ an \ event \ during \ treatment \ for \ period \ t, \\ and & D_t = & Number \ of \ patient-days \ of \ treatment \ for \ period \ t \ / \ 7 \end{array}$ 

IDs will also be calculated for each event for all 12 weeks during treatment combined  $(ID_A)$ , and the first week after stopping  $(ID_{SW1})$  if patient stopped (and where patients are recorded as remaining on treatment for at least 1 week) after index date.

Sensitivity analyses will examine any under-reporting by including events of interest recorded in primary care medical charts and confirmed on follow-up for those patients discharged to primary care, during the 12 week observation period.

As IDs for the overall cohort may sometimes mask significant signals in specific risk groups, the subgroups defined by specific characteristics (e.g. previous history of ACS or haemorrhage, previous/concurrent use of selected medications, off-label indication

<sup>1 It should be noted such quantification of rate does not only reflect the rate attributable to the drug but also reflects the background rate in the general population and rate attributable to other factors such as age or other disease risk factors

<sup>2 Ideally, the exposure time would be censored at the time of the first event. However, since there are a large number of health outcomes of interest and the censoring would be different for each outcome, the denominator for the crude ID will not initially include censoring. If an elevated crude ID is identified in this monitoring analysis, a subsequent analysis with appropriately censored denominator will be performed for that outcome.

groups, rivaroxaban naïve or past user) will have IDs calculated and compared according to strata for relevant events, where appropriate.

It is possible to explore the time taken for an event of interest using parametric time to event models (e.g. Weibull) as described previously, thus providing an additional tool for signal generation purposes. This approach will be explored for events of interest, where counts  $\geq 5$ . If undertaken, a sensitivity analysis will be performed to include in the numerator events reported within seven days of stopping, and extend the denominator by seven days.

# 9.7.5 To describe clinical features and management of cases of overdose, major bleeding (including bleeding sites specified in the primary objective, in addition to other major bleeds identified) (Tables 1 and 2) during observation of the cohort exposed to rivaroxaban.

The following relates to Section 8.2 exploratory objective 2) for the rivaroxaban cohort only. A qualitative assessment of these cases will include evaluation of patient demographic characteristics, treatment details, the detection and clinical features and management of events of interest, resolution, relevant investigations prior to and during therapy, the patient's relevant medical history and concurrent medication and any sequelae. Data will be derived from the SCEM and follow up questionnaires sent to gather other relevant essential information for construction of a case-series summary descriptive table.

Selected events of interest (Table 3) that require further characterisation and evaluation may be followed-up via a questionnaire sent to the responsible specialist HCP or patient's GP seeking further information. The information received at follow-up for events of medical significance or those which require further clarification will facilitate further evaluation at the aggregate level. Where it is appropriate to do so, drug relatedness assessments may be performed on selected events. The aim of the collective drug-relatedness assessment for groups of events during the analysis of the interim and final reports, is to put events in context regarding temporality co-morbidity, pre-existing disease and concomitant medications. This aggregate assessment of event data occurs at interim or final report for cases for which all requested information (i.e. baseline questionnaire, 12 week end of observation questionnaire and follow-up questionnaire if applicable) has been received. In the process of aggregate assessment of event data, the application of elements of the Austin Bradford Hill criteria, when the necessary information is available and the use of the method is considered appropriate, will be used (see Box 1).(18)

#### Box 1. Points for consideration in collective evaluation of reported events

- The distribution of time to onset (temporal relationship);
- The principle clinical and pathological characteristics of the group of events;
- The pharmacological plausibility based on previous knowledge of the drug and the therapeutic class if appropriate;
- Similar reports in medical literature
- patient's clinical characteristics, including:

- previous medical history, such as history of drug allergies, presence of renal or hepatic impairment, etc.

-concomitant medications or medications taken prior to and during treatment;

• Management and remedial action;

Where undertaken, the collective drug-relatedness of selected groups of events of interest will be categorised in terms of proportions of reports assessed within the following four categories: 1)  $probable^1$ , 2)  $possible^2$ , 3)  $unlikely^3$  and 4) not assessable.(19)

#### 9.7.6 Missingness

Missing data are those where a variable is directly reported as missing or unavailable, where a variable observation is blank, where the reported data may not be interpretable, or where the value must be imputed to be missing because of data inconsistency or out-of-range results. It is not possible to fully predict the pattern of missingness for each study variable; however several approaches will be initially undertaken to mitigate the potential for missingness in the process of data collection:

<sup>1 Events are assessed as 'probable' if the event is well defined clinically and pathologically, if there is a reasonable time sequence, if it is more likely to be attributed to the study drug rather than to a concurrent disease or concomitant medication, if there is a positive dechallenge, rechallenge or response to dose increase, and if there are other supporting criteria (e.g. on the basis of lab tests or histological findings).

<sup>2 Events are assessed as 'possible' if the event has a reasonable clinical and pathological definition, if there is a reasonable time sequence, if it could also be explained by concurrent disease or concomitant medication, but dechallenge, rechallenge and confirmatory investigations are inconclusive or not fully available. Medical judgement will be necessary in some cases.

<sup>3 Events are assessed as unlikely if the event had a temporal relationship to the study drug administration that made a causal relationship improbable, or if concurrent disease or concomitant medication provided a far more plausible explanation.

<sup>4 Events are unassessable if insufficient information about the event has been provided and an appropriate evaluation is therefore not possible.

1. Collection of data within questionnaires will be through use of closed questions with binary response (Y/N) where possible. Responders who are uncertain will be encouraged to review available information to provide suitable response.

2. Returned questionnaires will be examined upon receipt for data completeness. The responder will be contacted to obtain the missing or correct information and data revised as appropriate on source document when possible.

3. Reminders will be sent for those questionnaires where the document has not been received as anticipated in accordance with return dates.

4. Each patients' GP will be contacted to obtain information on key study variables – this supplementary information will contribute to identification of relevant cases, where information may be missing from questionnaires completed by specialists

Specific methods to handle issues of missing or conflicting data, will be summarised within the detailed study specific Data Management Plan (DMP) which will be constructed to assist database development and data analysis. In brief, the missingness pattern of primary covariates and proportions thereof in the study subjects will be presented to explore plausibility of missing at random (MAR) assumption to justify subsequent regression analysis. Multiple imputation is planned. However, we will compare the results of this to a complete case analysis. If the two are substantially different we will evaluate what the reasons may be. Thus, imputation will be performed using STATA SE 12 ICE imputation for exposure variables with less than 20% missing data and a sensitivity analysis conducted to determine magnitude and direction of bias arising from missing data from complete case analysis as relevant to Section 8.2 primary and secondary objectives.

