#### 9.2.5 Evaluable cohort

Evaluable patients are those patients who have provided consent and for whom analysable clinical data has been provided in the data collection questionnaires. Evaluable patients for whom the 12 week survey questionnaire (from both specialist HCP and GP) is returned blank (contain no clinical information) or has not been returned will Version 7 Date: 30/08/2017

only be included for analysis of secondary and exploratory objectives, where appropriate.

Consented patients will not be considered evaluable if the specialist HCP reports that the patient did not take either combination therapies. If there is evidence to suggest duplication of patients, either through inadvertent duplication between different prescribers within the same clinical setting, or if a patient was switched from one combination therapy to the other, then the records identified will be considered for inclusion on a case by case basis by the advisory committee.

Patients will be automatically withdrawn if the patient or specialist HCP provides informed written or verbal notification that they no longer wish to participate at any stage of the study.

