#### 9.3.5 Methods to Maximise Questionnaire Response Rate

Patient 12 week end of observation questionnaire

A proportion of Specialist HCPs or GPs are likely to fail to submit these questionnaires. Methods to maximise response rates will include prompts from study facilitators by phone, email and personal contact and reminder questionnaires targeted at those who have not responded within one month of the date the initial questionnaire was sent.

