For each individual case, relevant person-time will be estimated according to duration of observation up to event date. For each individual non-case, relevant person-time will estimated by either exit date – index date; or censor date – index date; or stop date (+ 2 days ) – index date. For each cohort separately, a semi-parametric time-dependent Cox Proportional Hazards regression model will be used to estimate the crude cumulative incidence over the 12 week observation period.

Non-parametric Kaplan-Meier plots will be presented to describe time-to event as well as smoothed estimates of the empirical hazard function to describe how the crude baseline risk of the event changes over time.

Estimates of the hazard function will also be modelled to determine whether the baseline hazard (risk) of the event increases or decreases with time. A constant hazard over time may be consistent with a background (not caused by the drug) event rate, whereas a non-constant hazard over time may be an indicator of a drug-event relationship. The null hypothesis that the hazard rate of the selected event in patients will be constant during the 12 week period following the start of treatment will be tested

<sup>1 This excludes patients prescribed rivaroxaban 2.5mg for non-ACS related indications

<sup>2 Censor date = date of loss to follow-up

<sup>3 2 days allocated to person-time to account for half-life of drug

Version 7 Date: 30/08/2017

by fitting a parametric time to event model (e.g. Weibull). Such models have a shape parameter that indicates whether the hazard is significantly increasing or decreasing over time. At least five reports of an event are deemed necessary for modelling purposes.

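### The planned comparison of imputed with complete-case results cannot show how much the overall crude primary incidence is biased by leaving out patients who have no usable 12-week form

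*Protocol*

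**What the plan says.** Section 9.2.5 covers evaluable patients whose "12 week survey questionnaire (from both specialist HCP and GP) is returned blank (contain no clinical information) or has not been returned". Such patients will "only be included for analysis of secondary and exploratory objectives, where appropriate", so they are outside the primary analysis.

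Section 9.7.1 analyses each cohort separately, using a Cox model to "estimate the crude cumulative incidence over the 12 week observation period". No adjustment covariate is named for that overall figure.

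Section 9.7.6 announces multiple imputation and a comparison with complete cases. It says that the missingness pattern of the primary covariates will be examined, and then specifies that "imputation will be performed using STATA SE 12 ICE imputation for exposure variables with less than 20% missing data". The same sentence adds "a sensitivity analysis conducted to determine magnitude and direction of bias arising from missing data from complete case analysis as relevant to" the primary and secondary objectives of Section 8.2. Specific methods for missing or conflicting data are deferred to a Data Management Plan, which is not part of the document.

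Section 9.3.5 foresees that "A proportion of Specialist HCPs or GPs are likely to fail to submit these questionnaires". Section 9.9 accepts that attrition and loss to follow-up may cause selection bias and relies on the short observation period to limit it.

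**The concern.** For an overall crude incidence, the missing item that matters most is the 12-week outcome itself, and the imputation step as written does not deal with it. A patient without a form has no outcome and is removed before the analysis starts. Filling in exposure variables for the remaining patients adds nothing about those who were removed.

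If form return is related to the patient's course (death, readmission or transfer of care, for example), the incidence among patients with a form differs from the incidence in the treated cohort, which is what the primary objective asks for. A report written to 9.7.6 could then set two similar figures side by side and present their agreement as evidence that missing data did not bias the primary result. That reassurance would not have been earned for this source of bias.

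**Working it through.** **1. The plan's own figure.** Section 9.5 gives 1193 patients per cohort to estimate 0.5% within +/-0.4 points (95% confidence interval).

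n = z²p(1-p)/d² = 1.96² × 0.005 × 0.995 / 0.004² = 1194.5

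With a finite-population correction, n/(1 + n/N), and N = 1,000,000 (inferred from other cells of Table 4; not stated in the protocol), this becomes 1193.0. The figure reproduces. It implies 1193 × 0.005 = 5.965, or about 6 primary events per cohort.

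**2. What the comparison can detect.** Let A be the patients with a usable form and E the evaluable patients with none.

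- Imputed analysis of the overall incidence: events in A divided by patients in A. The imputed covariates do not enter the figure.
- Complete-case analysis: the same ratio, either in all of A or in the part of A with complete covariates.

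Neither expression contains E. Any difference between them reflects covariate missingness within A. It does not respond to the risk in E, however high or low that is. The same holds for a survival estimate, because patients in E contribute neither events nor person-time.

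A simulation illustrates this. The assumptions were 1193 patients, 15% with no form, risk 1.5% without a form and 0.5% with one, 10% of an exposure covariate missing unrelated to outcome, and 2000 repeats. Average whole-cohort risk was 0.655% (by formula, 0.85 × 0.5% + 0.15 × 1.5% = 0.65%). The estimate with the exposure variable imputed averaged 0.505%, and the complete-case estimate 0.503%. The two agree, and both miss the gap of 0.15 points. This shows one case only; a covariate whose missingness was related to outcome could separate the two estimates.

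**3. Possible size of the bias.** Let r be the share of patients with no form and k their risk relative to the others. The protocol gives neither, so both are assumed. With p = 0.5% observed in patients with a form:

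- whole-cohort risk = p(1 - r + rk)
- relative bias of the reported figure = 1/(1 - r + rk) - 1

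| r | k | Whole-cohort risk | Relative bias |
|---|---|---|---|
| 10% | 0.5 | 0.475% | +5% |
| 10% | 2 | 0.55% | -9% |
| 10% | 3 | 0.60% | -17% |
| 20% | 0.5 | 0.45% | +11% |
| 20% | 2 | 0.60% | -17% |
| 20% | 3 | 0.70% | -29% |

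**4. Set against the planned precision.** The absolute bias equals the 0.4-point half-width when k = 1 + 0.004/(0.005r). That gives k = 17 at r = 5%, k = 9 at r = 10% and k = 5 at r = 20%. In every row of the table the shift is smaller than the half-width.

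**The case against.** **Scope of the imputation.** Section 9.7.6 does not say that only exposure variables will be imputed, its account is a summary, and details go to a Data Management Plan. Its definition of missing data is largely at variable level, so the step can be read as handling blank items, with unreturned forms dealt with openly by the rule in 9.2.5. This stands in part: outcome methods may be set out elsewhere. It does not remove the point, because the protocol itself names the method and says what it will show for the primary objective.

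**The primary section is more than one crude figure.** A reader might infer that imputed and complete-case results must agree throughout 9.7.1. The document does not support that. The section also has stratum-specific incidences, a univariate risk-factor analysis, a time-varying exposure covariate, and person-time that depends on index and stop dates. Imputation can change these. A complete-case set restricted on covariates could also shift the crude incidence. The point is confined to bias from patients with no form.

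**Expected non-return.** A reader might also infer from 9.3.5 that patients with no form at all are expected. That section speaks of specialists or GPs failing to respond, whereas exclusion requires that neither supplies a usable form. Joint failure should be rarer, and no rate is given. The GP safeguard is described unevenly: 9.3.3 and 9.4.2 make it depend on the care pathway, while 9.7.6 and 9.9 have every patient's GP contacted.

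**Mitigation.** Clinicians abstract the forms from charts, reminders are sent, reported deaths are followed up, and attrition is acknowledged. These steps reduce the number with no form but do not measure the bias from those who remain. The sensitivity analysis that ignores adjudication needs a reported event, and the under-reporting analyses in 9.7.3 and 9.7.4 need GP data. None reaches a patient with no form.

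**Materiality.** Every value of r and k is assumed, and the shifts shown are below the planned precision. This stands and limits the weight of the point.

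**Conclusion.** The point holds for the overall crude incidence. As specified, the comparison of imputed with complete-case results cannot show the magnitude or direction of bias from leaving out evaluable patients with no usable 12-week form, yet 9.7.6 presents it as determining missing-data bias for the primary objective.

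The size is unknown. For r of 10-20% and k of 0.5 to 3, all assumed, an observed 0.5% corresponds to about 0.45-0.70%. That is within the planned +/-0.4 points, but a confidence interval does not convey this kind of error, and with about 6 expected events per cohort one or two missed bleeds would matter. It would be wrong to conclude that the primary estimate is known to be biased, or that imputation has no use under 9.7.1. The plan should be corrected, but the fault does not invalidate the primary analysis.

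**What to change.** In section 9.7.6:

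1. State that the ICE comparison addresses missing exposure and covariate data only, and does not assess bias from patients without a 12-week form.
2. Report, by cohort, the number of evaluable patients with no usable form, and compare their baseline-questionnaire characteristics with those of the other patients.
3. Add a simple sensitivity analysis of the primary incidence. One option is bounds that give the excluded patients a range of multiples of the observed risk (for example 1, 2 and 3 times, and a value below 1). Another, if numbers allow, is inverse-probability-of-form-return weighting on a few baseline items.

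The cost is revised wording and a small extra analysis on baseline data already collected. The reported range will be wider, and with so few events any weighting model must stay simple.
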